## **5.7 Diet/Activity/Other Considerations**

### **5.7.1 Diet**

Subjects should maintain a normal diet unless modifications are required to manage an AE such as diarrhea, nausea or vomiting. Percutaneous endoscopic gastrostomy (PEG) tubes are acceptable for prophylactic feeding.

### **5.7.2 Contraception**

Pembrolizumab (MK-3475) may have adverse effects on a fetus in utero. Furthermore, it is not known if pembrolizumab (MK-3475) has transient adverse effects on the composition of sperm. Non-pregnant, non-breast-feeding women may be enrolled if they are willing to use 2 methods of birth control or are considered highly unlikely to conceive. Highly unlikely to conceive is defined as 1) surgically sterilized, or 2) postmenopausal (a woman who is  $\geq 45$  years of age and has not had menses for greater than 1 year will be considered postmenopausal), or 3) not heterosexually active for the duration of the study. The two birth control methods can either be two barrier methods or a barrier method plus a hormonal method to prevent pregnancy. Subjects should start using birth control from study Visit 1 throughout the study period up to 120 days after the last dose of study therapy.

The following are considered adequate barrier methods of contraception: diaphragm, condom (by the partner), copper intrauterine device, sponge, or spermicide. Appropriate hormonal contraceptives will include any registered and marketed contraceptive agent that contains an estrogen and/or a progestational agent (including oral, subcutaneous, intrauterine, or intramuscular agents).

Subjects should be informed that taking the study medication may involve unknown risks to the fetus (unborn baby) if pregnancy were to occur during the study. In order to participate in the study they must adhere to the contraception requirement (described above) for the duration of the study and during the follow-up period defined in Section 7.2.2-Reporting of Pregnancy and Lactation to the Sponsor. If there is any question that a subject will not reliably comply with the requirements for contraception, that subject should not be entered into the study.

### **5.7.3 Use in Pregnancy**

If a subject inadvertently becomes pregnant while on treatment with pembrolizumab (MK-3475), the subject will immediately be removed from the study. The site will contact the subject at least monthly and document the subject's status until the pregnancy has been completed or terminated. The outcome of the pregnancy will be reported to the Sponsor without delay and within 24 hours if the outcome is a serious adverse experience (e.g., death, abortion, congenital anomaly, or other disabling or life-threatening complication to the mother or newborn). The study investigator will make every effort to obtain permission to follow the outcome of the pregnancy and report the condition of the fetus or newborn to the Sponsor. If a male subject impregnates his female partner the study personnel at the site must be informed immediately and the pregnancy reported to the Sponsor and followed as described above and in Section 7.2.2.

#### **5.7.4 Use in Nursing Women**

It is unknown whether pembrolizumab (MK-3475) is excreted in human milk. Since many drugs are excreted in human milk, and because of the potential for serious adverse reactions in the nursing infant, subjects who are breast-feeding are not eligible for enrollment.

### **5.8 Subject Withdrawal/Discontinuation Criteria**

Subjects may withdraw consent at any time for any reason or be dropped from the trial at the discretion of the investigator should any untoward effect occur. In addition, a subject may be withdrawn by the investigator or the Sponsor if enrollment into the trial is inappropriate, the trial plan is violated, or for administrative and/or other safety reasons. Specific details regarding discontinuation or withdrawal procedures; including specific details regarding withdrawal from Future Biomedical Research, are provided in Section 7.1.4 – Other Procedures.

In this trial, a subject may discontinue from treatment but continue to participate in the regularly scheduled activities, as long as the subject does not withdraw consent. Once a subject has discontinued treatment, even though he/she continues to be monitored in the trial, he/she may be allowed to begin treatment again if deemed medically appropriate.

A subject must be discontinued from the trial for any of the following reasons:

- The subject or legal representative (such as a parent or legal guardian) withdraws consent.

A subject must be discontinued from treatment (but may continue to be monitored in the trial) for any of the following reasons:

- The subject or legal representative (such as a parent or legal guardian) withdraws consent for treatment
- Confirmed radiographic disease progression

*Note:* For unconfirmed radiographic disease progression, please see Section 5.2.2.

*Note:* A subject may be granted an exception to continue on treatment with confirmed radiographic progression if clinically stable or clinically improved, please see Section 7.1.2.6.3.

- Unacceptable adverse experiences as described in Section 5.2.1.2
- Intercurrent illness that prevents further administration of treatment
- Investigator's decision to withdraw the subject
- The subject has a confirmed positive serum pregnancy test

- Noncompliance with trial treatment or procedure requirements
- The subject is lost to follow-up
- Completed 24 months of treatment with pembrolizumab (MK-3475)

*Note: 24 months of study medication is calculated from the date of first dose. Subjects who stop pembrolizumab (MK-3475) after 24 months may be eligible for up to one year of additional study treatment if they progress after stopping study treatment provided they meet the requirements detailed in Section 7.1.5.2.1.*

- Administrative reasons

The End of Treatment and Follow-up visit procedures are listed in Section 6 (Protocol Flow Chart) and Section 7.1.5 (Visit Requirements). After the end of treatment, each subject will be followed for 30 days for adverse event monitoring (serious adverse events and events of clinical interest will be collected for 90 days after the end of treatment or 30 days after the end of treatment if the subject initiates new anticancer therapy, whichever is earlier, as described in Section 7.2.3.1). Subjects who discontinue study drug for reasons other than progressive disease will have post-treatment follow-up for disease status until end of study disease progression, initiating a non-study cancer treatment, withdrawing consent or becoming lost to follow-up. After documented disease progression each subject will be followed by telephone for overall survival until death, withdrawal of consent, or the end of the study, whichever occurs first.

### **5.8.1 Discontinuation of Study Therapy after CR**

Discontinuation of treatment may be considered for subjects who have attained a confirmed CR that have been treated for at least 24 weeks with pembrolizumab (MK-3475) and had at least two treatments with pembrolizumab (MK-3475) beyond the date when the initial CR was declared. Subjects who then experience radiographic disease progression may be eligible for up to one year of additional treatment with pembrolizumab (MK-3475) at the discretion of the investigator if no cancer treatment was administered since the last dose of pembrolizumab (MK-3475), the subject meets the safety parameters listed in the Inclusion/Exclusion criteria, and the trial is open. Subjects will resume therapy at the same dose and schedule at the time of initial discontinuation. Additional details are provided in Section 7.1.5.2.1.

### **5.9 Subject Replacement Strategy**

A subject who discontinues from the trial will not be replaced.

### **5.10 Beginning and End of the Trial**

The overall trial begins when the first subject signs the informed consent form. The overall trial ends when the last subject completes the last study related phone call or visit, discontinues from the trial or is lost to follow-up (i.e. the subject is unable to be contacted by the investigator). Upon study completion, subjects are discontinued and enrolled in a pembrolizumab extension trial.

## **5.11 Clinical Criteria for Early Trial Termination**

There are no pre-specified criteria for terminating the trial early.

The clinical trial may be terminated early if the extent (incidence and/or severity) of emerging effects/clinical endpoints is such that the risk/benefit ratio to the trial population as a whole is unacceptable. In addition, further recruitment in the trial or at (a) particular trial site(s) may be stopped due to insufficient compliance with the protocol, GCP and/or other applicable regulatory requirements, procedure-related problems or the number of discontinuations for administrative reasons is too high.

Early trial termination will be the result of the criteria specified below:

1. Quality or quantity of data recording is inaccurate or incomplete
2. Poor adherence to protocol and regulatory requirements
3. Incidence or severity of adverse drug reaction in this or other studies indicates a potential health hazard to subjects
4. Plans to modify or discontinue the development of the study drug

In the event of Sponsor decision to no longer supply study drug, ample notification will be provided so that appropriate adjustments to subject treatment can be made.

## 6.0 TRIAL FLOW CHART

### 6.1 Initial Treatment Phase and Second Course Phase (Retreatment)

#### 6.1.1 Initial Treatment Phase

Trial Period:	Screening Phase	Treatment Cycles a						End of Treatment	Post-Treatment		
		1	2	3	4	To be repeated beyond 6 cycles		Discon	Safety Follow-up	Follow Up Visits b	Survival Follow-up c
Treatment Cycle/Title:	Screening (Visit 1)					5	6				
Scheduling Window (Days) d :	-42 to -1	-28 to -1	+3 d	± 3	± 3	± 3	± 3	At time of discon	30 days post discon	Every 6 weeks post discon	Approx. every 12 weeks
Administrative Procedures											
Informed Consent	X e										
Informed Consent for Future Biomedical Research		X f									
Inclusion/Exclusion Criteria		X									
Subject Identification Card		X									
Demographics and Medical History		X									
Prior and Concomitant Medication Review g	X	X	X	X	X	X	X	X	X		
Trial Treatment Administration h		X	X	X	X	X	X				
Post-study Anticancer Therapy Status										X	X
Survival Status c											X
Clinical Procedures/Assessments											
Review Adverse Events	X	X	X	X	X	X	X	X	X i	X i	
12-Lead ECG (Local) x	X										
Full Physical Examination x	X							X			
Directed Physical Examination		X	X	X	X	X	X				
Vital Signs and Weight k	X	X	X	X	X	X	X	X	X	X	
ECOG Performance Status	X	X	X	X	X	X	X	X	X	X	
Laboratory Procedures/Assessments: analysis performed by LOCAL laboratory											
Pregnancy Test – Serum or Urine l		X									
PT/INR and aPTT m		X n									
CBC with Differential o		X n		X	X	X	X	X	X p		
Chemistry Panel o		X n		X	X	X	X	X	X p		

Trial Period:	Screening Phase	Treatment Cycles a						End of Treatment	Post-Treatment		
		1	2	3	4	To be repeated beyond 6 cycles		Discon	Safety Follow-up	Follow Up Visits b	Survival Follow-up c
Treatment Cycle/Title:	Screening (Visit 1)					5	6				
Scheduling Window (Days) d :	-42 to -1	-28 to -1	+3 d	± 3	± 3	± 3	± 3	At time of discon	30 days post discon	Every 6 weeks post discon	Approx. every 12 weeks
Urinalysis o		X n		X		X	X t		X p		
T3, FT4 and TSH o		X n		X		X	X t		X p		
HPV Status w	X										
Laboratory Procedures/Assessments: analysis performed by CENTRAL laboratory											
Pharmacokinetics q			X q	X q		X q					
Anti-MK-3475 Antibodies q			X q	X q		X q					
Correlative Blood Samples r			X	X	X				X		
Blood for Genetics v			X								
Efficacy Measurements											
Tumor Imaging		X s				X t		X t		X b	
Tumor Tissue Collection											
Newly Obtained Tissue Collection	X u										
a. In general, assessments/procedures are to be performed on Day 1 and prior to the first dose of treatment for each cycle unless otherwise specified. Treatment cycles are 3 weeks. Imaging should be performed at 9 weeks after 1 st dose and every 6 weeks thereafter (42 days ± 7 days) regardless of any treatment delays. After 1 year, imaging will occur every 9 weeks (± 7 days). b. In subjects who discontinue study therapy without documented disease progression, every effort should be made to continue monitoring their disease status every 6 weeks (± 7 days) in the first year and every 9 weeks (± 7 days) after year 1 until (1) the start of new anti-cancer treatment, (2) disease progression, (3) death, or (4) notified by the Sponsor, whichever occurs first. If imaging assessment beyond the protocol-required imaging time frame is necessary, the reason for the extended imaging schedule should be documented in the subject's chart and recorded in the Oncologic Response-Solid Tumor (ORST) eCRF for each imaging assessment completed within the extended time frame. The maximum imaging time frame allowed is no greater than twice the imaging time frame noted for the specific year of follow-up (ie, first year follow-up is every 6 weeks; the maximum imaging schedule allowance is every 12 weeks. Second year follow-up is every 9 weeks; the maximum imaging schedule allowance is every 18 weeks). Every effort should be made to target the protocol-required imaging schedule as closely as possible; however, in the interest of the subject's continued participation in the follow-up phase of the study, the extended imaging time frame may be considered at the discretion of the investigator. c. After the start of new anti-cancer treatment or documented local site-assessed disease progression, the subject should be contacted by telephone approximately every 12 weeks to assess for survival status. Updated survival status may be requested by the Sponsor at any time during the course of the trial. Upon Sponsor notification, all subjects who do not/will not have a scheduled trial visit or trial contact during the Sponsor-defined time period will be contacted for their survival status (excluding subjects who have a death event previously recorded). d. In general, the window for each visit is ± 3 days unless otherwise noted. Cycle 1 treatment must be given within 3-5 days of enrollment. e. Written consent must be obtained prior to performing any protocol specified procedure. Please note that the window for acquiring the "newly obtained" tissue specimen is within 42 days of the first dose of study drug and written consent should be obtained prior to acquiring the specimen if a biopsy for the study is performed. Results of a test performed prior to the subject signing consent as part of routine clinical management are acceptable in lieu of a screening test if performed within the window specified for screening procedures (e.g., within 28 days											

Trial Period:	Screening Phase	Treatment Cycles a						End of Treatment	Post-Treatment		
		1	2	3	4	To be repeated beyond 6 cycles			Discon	Safety Follow-up	Follow Up Visits b
Treatment Cycle/Title:	Screening (Visit 1)					5	6				
Scheduling Window (Days) d :	-42 to -1	-28 to -1	+3 d	± 3	± 3	± 3	± 3	At time of discon	30 days post discon	Every 6 weeks post discon	Approx. every 12 weeks
prior to the first dose of trial treatment for required lab tests). Screening number will be assigned when the study informed consent is signed. 
 
f. Signing the informed consent for future biomedical research (FBR) sample is optional. Detailed instructions for the collection and management of specimens for FBR are provided in the appendices of the Central Lab Manual and Section 12.2 of the Protocol.
 
g. Prior medications – Record all medications taken within 30 days of the screening visit. Concomitant medications – Enter new medications started during the trial through the Safety Follow-up visit. Record all medications taken for SAEs as defined in Section 7.2.
 
h. Trial treatment may be administered up to 3 days before or after the scheduled Day 1 of each cycle due to administrative reasons. Sites should make every effort to target infusion timing to be as close to 30 minutes as possible. However, given the variability of infusion pumps from site to site, a window of -5 minutes and +10 minutes is permitted (i.e., infusion time is 30 minutes: -5 min/+10 min). The reason for any delay in infusion outside of the protocol specified window should be documented in the patient's chart and recorded on the eCRFs.
 
i. Record all AEs occurring within 30 days after the last dose of trial treatment. Report all SAEs (related and unrelated to trial treatment) and ECIs occurring up until 90 days after the last dose of trial treatment or the start of new anti-cancer treatment, whichever comes first. Afterwards, report only SAEs and ECIs that are related to trial treatment.
 
j. To be repeated every 2 cycles after Cycle 6 up to 1 year.
 
k. Vital signs to include temperature, pulse, respiratory rate, weight and blood pressure. Height will be measured at visit 1 only.
 
l. For women of reproductive potential, a serum pregnancy test should be performed within 72 hours prior to first dose of trial treatment. A urine test can be considered if serum is not appropriate. Pregnancy tests (serum and/or urine tests) should be repeated if required by local guidelines.
 
m. Coagulation factors (PT/INR and aPTT) should be tested as part of the screening procedures for all subjects. Any subject receiving anticoagulant therapy should have coagulation factors monitored closely throughout the trial.
 
n. Laboratory tests for screening are to be performed within 10 days prior to the first dose of trial treatment. See Section 7.1.3 for details regarding laboratory tests.
 
o. After Cycle 1, lab samples can be collected up to 72 hours prior to the scheduled time point. See Section 7.1.3 for details regarding laboratory tests.
 
p. Unresolved abnormal labs that are drug related AEs should be followed until resolution. Labs do not need to be repeated after the end of treatment if labs are within normal range.
 
q. Pre-dose trough PK and anti-pembrolizumab (MK-3475) antibody samples will be collected at Cycles 1, 2, 4, 8, and every 4 cycles thereafter. All pre-dose trough samples should be drawn within 24 hours before infusion of pembrolizumab (MK-3475). Additional post-dose peak PK samples will be drawn within 30 minutes after end of pembrolizumab (MK-3475) infusion at Cycles 1 and 8. An additional, single PK sample should be drawn between 72 and 168 hours after Cycle 1 dosing.
 
r. Blood for correlative studies should be collected prior to Cycle 1, Cycle 2, Cycle 3 and again at treatment discontinuation.
 
s. The initial tumor imaging will be performed within 28 days prior to the first dose of trial treatment and must be sent to the central vendor to confirm measurable disease for study eligibility. Imaging should include the head, neck, chest, and abdomen; imaging of the pelvis is optional (refer to Section 7.1.2.6). Scans performed as part of routine clinical management are acceptable for use as the screening scan if they are of diagnostic quality, meet the requirements specified by the protocol, and are performed within 28 days prior to the first dose of trial treatment.
 
t. The first on-study imaging time point will be performed at 9 weeks (± 7 days) after first dose of study treatment and then every 6 weeks (± 7 days) thereafter or more frequently if clinically indicated. After 1 year, imaging time point will occur every 9 weeks (± 7 days). Imaging timing should follow calendar days and should not be adjusted for delays in cycle starts or extension of pembrolizumab (MK-3475) cycle frequencies. Imaging should include the head, neck, chest, and abdomen; imaging of the pelvis is optional (refer to Section 7.1.2.6). The same imaging technique should be used in a subject throughout the trial. On-study scans, including the baseline scans, should be submitted immediately to the central imaging vendor.
 
u. Baseline tumor tissue for biomarker analysis from a newly obtained core or excisional biopsy (FNA not adequate) must be provided to the central vendor for PD-L1 biomarker testing. Confirmation of tissue adequacy should be received from the central vendor prior to the first dose of trial treatment. A “newly obtained” sample may be obtained up to 42 days prior to
 
											

Trial Period:	Screening Phase	Treatment Cycles a						End of Treatment	Post-Treatment		
		1	2	3	4	To be repeated beyond 6 cycles			Discon	Safety Follow-up	Follow Up Visits b
Treatment Cycle/Title:	Screening (Visit 1)					5	6				
Scheduling Window (Days) d :	-42 to -1	-28 to -1	+3 d	± 3	± 3	± 3	± 3	At time of discon	30 days post discon	Every 6 weeks post discon	Approx. every 12 weeks

treatment initiation. Tissue beyond the 42-day window may be considered with Sponsor approval as long as no intervening systemic therapy has been administered. Tissue that has been previously irradiated is acceptable. Detailed instructions for tissue collection, process and shipment are provided in the appendices of the Central Lab Manual. If the subject signs the Future Biomedical Research (FBR) consent, any leftover tissue that would ordinarily be discarded at the end of the main study will be retained for FBR.
 
v. This sample should be drawn for planned, exploratory genetic analysis of DNA unless there is either a documented law or regulation prohibiting collection, or unless the IRB/IEC does not approve of the collection. If the sample is collected, any leftover extracted DNA will be stored for future biomedical research if the subject signs the optional Future Biomedical Research consent.
 
w. Subjects with oropharynx cancer must have an assessment of HPV status from tumor tissue. Any prior HPV status included in the patient's medical history may be used.
 
x. In the event that a screening assessment is delayed due to a central vendor assessment (i.e. assessment of measureable disease by the central imaging vendor or assessment of tumor adequacy), Sponsor approval may be granted to allow testing outside of the visit window.
											

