- All subjects who experience diarrhea/colitis should be advised to drink liberal quantities of clear fluids. If sufficient oral fluid intake is not feasible, fluid and electrolytes should be substituted via IV infusion. For Grade 2 or higher diarrhea, consider GI consultation and endoscopy to confirm or rule out colitis.
- For **Grade 2 diarrhea/colitis** that persists greater than 3 days, administer oral corticosteroids.
- For **Grade 3 or 4 diarrhea/colitis** that persists > 1 week, treat with intravenous steroids followed by high dose oral steroids.
- When symptoms improve to Grade 1 or less, steroid taper should be started and continued over no less than 4 weeks.

- **Type 1 diabetes mellitus (if new onset, including diabetic ketoacidosis [DKA]) or  $\geq$  Grade 3 Hyperglycemia, if associated with ketosis (ketonuria) or metabolic acidosis (DKA)**

- For **T1DM or Grade 3-4 Hyperglycemia**
  - Insulin replacement therapy is recommended for Type I diabetes mellitus and for Grade 3-4 hyperglycemia associated with metabolic acidosis or ketonuria.
  - Evaluate patients with serum glucose and a metabolic panel, urine ketones, glycosylated hemoglobin, and C-peptide.

• **Hypophysitis:**

- For **Grade 2** events, treat with corticosteroids. When symptoms improve to Grade 1 or less, steroid taper should be started and continued over no less than 4 weeks. Replacement of appropriate hormones may be required as the steroid dose is tapered.
- For **Grade 3-4** events, treat with an initial dose of IV corticosteroids followed by oral corticosteroids. When symptoms improve to Grade 1 or less, steroid taper should be started and continued over no less than 4 weeks. Replacement of appropriate hormones may be required as the steroid dose is tapered.

• **Hyperthyroidism or Hypothyroidism:**

Thyroid disorders can occur at any time during treatment. Monitor patients for changes in thyroid function (at the start of treatment, periodically during treatment, and as indicated based on clinical evaluation) and for clinical signs and symptoms of thyroid disorders.

- **Grade 2** hyperthyroidism events (and **Grade 2-4** hypothyroidism):
  - In hyperthyroidism, non-selective beta-blockers (e.g. propranolol) are suggested as initial therapy.
  - In hypothyroidism, thyroid hormone replacement therapy, with levothyroxine or liothyronine, is indicated per standard of care.
- **Grade 3-4** hyperthyroidism

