f.	Concomitant medications – Enter new medications started during the trial through the Safety Follow-up visit. Record all medications taken for AEs as defined in Section 7.2.									
g.	Subjects who restart treatment should resume at the same dose and cycle interval which they were receiving prior to discontinuation.									
h.	AEs and laboratory safety measurements will be graded per NCI CTCAE version 4.0. All AEs, whether gradable by CTCAE or not, will also be evaluated for seriousness.									
i.	Record all AEs occurring within 30 days after the last dose of trial treatment. Report all SAEs (related and unrelated to trial treatment) and ECIs occurring up until 90 days after the last dose of trial treatment or 30 days after the start of new anti-cancer treatment, whichever comes first. Afterwards, report only SAEs and ECIs that are related to trial treatment.									
j.	To be repeated every 2 cycles after Cycle 5.									
k.	Vital signs to include temperature, pulse, respiratory rate, weight and blood pressure. Height will be measured at visit 1 only.									
l.	For women of reproductive potential, a serum pregnancy test should be performed within 72 hours prior to first dose of retreatment. A urine test can be considered if serum is not appropriate. Pregnancy tests (serum and/or urine tests) should be repeated if required by local guidelines.									
m.	Coagulation factors (PT/INR and aPTT) should be monitored closely throughout the trial for any subject receiving anticoagulant therapy.									
n.	Laboratory tests for determining eligibility for retreatment are to be performed within 10 days prior to the first retreatment dose of pembrolizumab. See Section 7.1.3 for details regarding laboratory tests.									
o.	After Cycle 1, lab samples can be collected up to 72 hours prior to the scheduled time point. See Section 7.1.3 for details regarding laboratory tests. T3 or FT3 can be assayed based on local standards.									

Trial Period:	Treatment Cycles (3-Week Cycles) a						End of Treatment	Post-Treatment		
	1	2	3	4	To be repeated beyond 6 cycles	Discon		Safety Follow-up	Follow Up Visits b	Survival Follow-up c
Treatment Cycle/Title:	5	6								
Scheduling Window (Days) d :	+3 d	± 3	± 3	± 3	± 3	± 3	At time of discon	30 days post discon	Every 6 weeks post discon or per footnote	Approx. every 12 weeks

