**AND**

- Experienced an investigator-determined confirmed radiographic disease progression after stopping their initial treatment with pembrolizumab (MK-3475)
- Did not receive any anti-cancer treatment since the last dose of pembrolizumab (MK-3475)
- Has a performance status of 0 or 1 on the ECOG Performance Scale
- Demonstrates adequate organ function as detailed in Section 5.1.2
- Female subject of childbearing potential should have a negative serum or urine pregnancy test within 72 hours prior to receiving retreatment with study medication.
- Female subject of childbearing potential should be willing to use 2 methods of birth control or be surgically sterile, or abstain from heterosexual activity for the course of the study through 120 days after the last dose of study medication (Reference Section 5.7.2). Subjects of child bearing potential are those who have not been surgically sterilized or have been free from menses for > 1 year.
- Male subject should agree to use an adequate method of contraception starting with the first dose of study therapy through 120 days after the last dose of study therapy.
- Does not have a history or current evidence of any condition, therapy, or laboratory abnormality that might interfere with the subject's participation for the full duration of the trial or is not in the best interest of the subject to participate, in the opinion of the treating investigator.

Subjects who restart treatment will be retreated at the same dose frequency as when they last received pembrolizumab (MK-3475). Treatment will be administered for up to one additional year.

Visit requirements are outlined in Section 6.0 – Trial Flow Chart.

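### Section 6.1.1, footnote j: on the best reading, scheduled on-treatment thyroid tests stop at about Cycle 18, although initial treatment may run to Cycle 35 and Section 5.6 asks for periodic monitoring

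*Combined protocol and SAP*

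**What the plan says.** The flow chart in Section 6.1.1 lists T3, FT4 and TSH as local laboratory tests at screening, on alternate early cycles, in the repeating-cycle column and once after treatment. Footnote j states a repeat rule: "To be repeated every 2 cycles after Cycle 6 up to 1 year". The general column header over the later cycles is "To be repeated beyond 6 cycles", with no time limit. Footnote p lets the post-treatment laboratory tests be skipped when results are normal.

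Section 5.8 ends initial treatment at 24 months, counted from the first dose. Footnote a sets the cycle length at 3 weeks.

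On thyroid disorders, Section 5.6 says "Thyroid disorders can occur at any time during treatment" and asks for thyroid function to be monitored "at the start of treatment, periodically during treatment, and as indicated based on clinical evaluation".

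In the second-course chart (Section 6.1.2) the thyroid row is marked j, and footnote j there reads "To be repeated every 2 cycles after Cycle 5". Section 7.1.5.2.1 limits that course: "Treatment will be administered for up to one additional year".

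**The concern.** If the 1-year limit applies to the thyroid row, a subject in months 13 to 24 of initial treatment has no thyroid test on the schedule while still being dosed every 3 weeks. Section 5.6 describes a risk that lasts as long as treatment does. It also lists periodic monitoring separately from testing on clinical grounds, so testing prompted only by symptoms does not fully meet it. The documents give no reason for a stop at 1 year. Imaging, by comparison, becomes less frequent after 1 year but does not end.

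What is at stake is earlier detection. Table 3 calls for hormone replacement in Grade 2 to 4 hypothyroidism, and for holding or stopping pembrolizumab in Grade 3 or 4 hyperthyroidism. A scheduled test can show a disorder before symptoms prompt one. Safety and tolerability form the first primary objective (Section 3.1).

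**Working it through.** **Step 1. Does footnote j govern the thyroid row?** The table is damaged: its scheduling row shows five treatment windows for six cycles. The marker therefore has to be inferred.

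- Footnotes a to x are all defined. In the chart as we have it, every letter is attached to a row, cell or header except j.
- The repeating-cycle cell of the thyroid row, and of the urinalysis row, shows t. Footnote t concerns imaging and cannot apply to a laboratory test.
- Both rows are filled on alternate cycles, which fits a rule of every 2 cycles after Cycle 6. CBC and chemistry are filled every cycle.
- The thyroid row in Section 6.1.2 carries j, with a rule of the same form.

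These four facts make j the best reading. The printed t may be a fault of text extraction and is not held against the plan.

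**Step 2. When does scheduled testing stop?** Assume no dose delays. Cycle k starts on day 21(k − 1) + 1.

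- Last cycle by day 365: k = 18, since 21 × 17 + 1 = 358. Cycle 18 is even, so it is also a test cycle.
- The next test cycle would be Cycle 20: 21 × 19 + 1 = day 400, past 1 year even with the 3-day visit window.
- Last cycle by day 730: k = 35, since 21 × 34 + 1 = 715.
- Using 52 and 104 weeks in place of 365 and 730 days gives the same two cycles.

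**Step 3. Size of the gap in the initial phase.**

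- Scheduled on-treatment tests, even cycles 2 to 18: 9.
- Doses at Cycles 19 to 35: 35 − 18 = 17, and 17/35 = 49%.
- Last scheduled test to last dose: 715 − 358 = 357 days = 51 weeks.

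| Treatment stops at | Last cycle | Doses after Cycle 18 |
|---|---|---|
| 1 year or earlier | 18 or lower | 0 |
| 15 months | 22 | 4 |
| 18 months | 27 | 9 |
| 21 months | 31 | 13 |
| 24 months | 35 | 17 |

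**Step 4. With the limit removed.** Tests are added at Cycles 20, 22, ..., 34, which is 8 tests. Cycle 34 falls on day 21 × 33 + 1 = 694, so one dose (Cycle 35) follows the last test, 3 weeks later.

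**Step 5. Does anything else schedule a thyroid test in year 2?** No other section does. The post-treatment test comes after the last dose. Footnote p does not say how recent a normal result must be for that test to be waived, and the latest scheduled thyroid result could be the one from Cycle 18.

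**The case against.** The strongest objection is to the premise. The marker and the alternate-cycle layout are both reconstructed from a broken table. If j does not apply to the thyroid row, the column header leaves testing open-ended and there is no gap. This stands as a limit on confidence. It does not displace the reading, because no other row needs footnote j and the marker shown cannot be right.

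The second objection is that nothing is really missing. Section 5.6 carries no 1-year limit, sets no interval, calls its measures suggested, and still applies in year 2. Table 3 asks for clinical watchfulness for thyroid disease, whereas for liver events it names laboratory tests. Section 7.2.3.2 requires an assessment for events of clinical interest before each dose, including laboratory review and questions about symptoms. Section 7.1 allows unscheduled tests. The separate guidance document on events of clinical interest, not available here, may add monitoring. All of this softens the gap, and it rules out a flat contradiction between sections. But none of the text available places a thyroid test on the schedule after Cycle 18, and a laboratory review can only consider tests that were drawn.

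The third objection is to importance, and most of it stands. The 49% is the extreme case of a subject who completes 24 months, and the documents do not say how many will pass 1 year. Much of what a routine test alone finds would be Grade 1, for which Table 8 indicates no intervention. For Grade 2 to 4 hypothyroidism, Table 3 continues pembrolizumab. The safety summary in Section 4.1.3 names no thyroid event in the 60-patient cohort, and the follow-up described there is too short to give a year-2 rate.

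**Conclusion.** The point holds as a minor one, with medium confidence: on the best reading of footnote j, scheduled on-treatment thyroid testing covers roughly the first half of the longest permitted initial course. The gap ranges from no doses for subjects who stop by 1 year to 17 doses over 51 weeks for those who complete 24 months. It rests on footnote j governing the row and on dosing without delays.

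A reader might infer three stronger things that the documents do not support.

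- That thyroid testing ends altogether at 1 year. It does not: a post-treatment test remains, subject to footnote p, and sites may test at any time.
- That the second-course chart shows testing was meant to continue through a second year. That course is itself limited to one year, so a 1-year limit there would be redundant. It schedules 9 tests (Cycles 1, 3, ..., 17) over 18 doses, and it is no precedent for a second continuous year.
- That a countable number of thyroid events would be missed. Year-2 event rates cannot be estimated from the documents.

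The efficacy analysis is untouched: ORR, power and alpha do not depend on this schedule.

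**What to change.** In footnote j of Section 6.1.1, remove the 1-year limit for T3/FT4/TSH, so that testing runs every 2 cycles to the end of initial treatment. If the same footnote also governs urinalysis, that row can keep the limit, because Section 5.6 makes no matching request for it. When making the edit, confirm that the thyroid row carries the j marker. If it does not, stating the frequency explicitly does no harm.

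The cost is a footnote edit and at most 8 extra local thyroid panels per subject who completes year 2, with none for subjects who stop by 1 year. CBC and chemistry are already drawn at those visits, so no extra visit or separate blood draw is needed.
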